### **3.7. Recording Adverse Events**

Adverse events spontaneously reported by the subject and/or in response to an open question from the study personnel or revealed by observation, regardless of severity or potential association with the study medication or study procedures, will be recorded in the eCRF. Clinically significant changes in blood pressure and heart rate should be reported as AEs; however, Omega-3 treatment has been demonstrated to have beneficial effects on blood pressure and heart rate. Only clinically significant changes (increase or decrease) in heart rate should be reported as AEs. All AEs that occur after a subject has signed the informed consent form until the final study visit, Visit 4 (Day 84), should be collected and recorded on the AE eCRF page. AEs that occur after informed consent is provided but before the first dose of study medication will be summarized separately from AEs that occur from the first dose of double-masked treatment on Day 0 to the Day 84 visit. Serious adverse events will be followed until the event is resolved or stabilized.

Medical conditions/diseases occurring before the signing of Informed Consent Form during Visit 1 (Screening) should be collected on the medical/ocular history pages of the eCRF.

The AE term should be reported in standard medical terminology when possible. For each AE, the Investigator will evaluate and report the following:

- Onset (date and time);
- Resolution (date and time);
- Severity grade (mild, moderate, severe);
- Relationship to study medication (not suspected, suspected);
- Action taken (none, study medication temporarily interrupted, study medication permanently discontinued; concomitant medication taken; hospitalization/prolonged hospitalization; other);
- Serious outcome (yes/no).

The severity grade should be determined by the Investigator using the definitions below.

- Mild: Discomfort noticed but no disruption of normal daily activity
- Moderate: Discomfort sufficient to cause interference with normal daily activity
- Severe: Incapacitating, with inability to perform normal activities

**Table 2: Schedule of Procedures**

Procedures	Visit 1 Screening	Visit 2 Baseline	Visit 3	Visit 4/Early Discontinuation
Days	-7 to -1	0	42 ± 7 days	84 ± 7 days
Informed consent	X			
Demographics	X			
Medical/ocular history	X			
Concomitant medication history/review	X	X	X	X
Urine pregnancy test a	X			X
Ocular Surface Disease Index Questionnaire		X		X
Tear osmolarity	X	X		X
Meibomian gland dysfunction grading at slit-lamp using meibomian orifice size and telangiectasia scales	X	X		X
Slit-lamp examination		X	X	X
Tear break-up time (TBUT)	X	X		X
Schirmer's test (anesthetized)	X			X
Review inclusion/exclusion criteria	X	X		
Randomization		X		
HS-Omega-3 Index Test (fingerstick)		X		X
Study medication and study medication diary distribution		X	X	
Adverse event assessment b	X	X	X	X
Study medication accountability c		X	X	X
Study medication diary review			X	X

a Women of childbearing potential only.

b Collection of AEs extends from signing of informed consent until the last study visit.

c Clinical site personnel will document all dispensed or returned study medication as applicable at Baseline, and Days 42 and 84.

#### **4. SAMPLE SIZE AND POWER CONSIDERATIONS**

TBUT: A sample size of 82 in each group will have 95% power to detect a difference in means of 2.07 seconds assuming that the common standard deviation is 3.5 using a two-group t-test with a 0.05 two-sided significance level.

OSDI: A sample size of 82 in each group will have approximately 95% power to detect a difference in means of 11.390 assuming that the common standard deviation is 20.0 using a two-group t test with a 0.05 two-sided significance level.

When 90 subjects have completed treatment a review of treatment compliance will be conducted. If more than 10% of subjects have protocol deviations for treatment compliance, the study will be resized to achieve a study population in which 90% are compliant.

## **5. ANALYSIS POPULATIONS**

### **5.1.1. Populations for Efficacy Analysis**

#### **5.1.1.1. Intent-to-Treat Population**

The intent-to-treat (ITT) population is defined as all randomized subjects. The primary efficacy analysis will be performed on the ITT population.

#### **5.1.1.2. Per Protocol Population**

The per protocol (PP) population will include all ITT subjects who remain in the study through Visit 4 and who did not deviate from the protocol in any way likely to seriously affect the primary outcome of the study. Secondary efficacy analyses will be performed on the PP population.

### **5.1.2. Safety Analysis Population**

The safety population will include all subjects who have received at least one dose of the study medication. All safety analyses will utilize the safety population.

## **6. HANDLING OF MISSING DATA**

The planned statistical methods use all available data. To account for the presence of missing data, multiple imputation may be used for ITT analyses on the primary endpoints. Multiple imputation will be carried out using the SAS procedures.

## 7. STATISTICAL ANALYSIS

Efficacy analysis will be conducted on the ITT population and on the PP population. Safety analyses will be performed using the safety analysis population.

The study eye will be the worse of qualifying eyes at Baseline as defined by lower TBUT score; if both eyes score equally on TBUT, the eye with the higher tear osmolarity score will be chosen, and if still equal the right eye will be the study eye. All statistical analyses and reporting will be performed using the SAS® System Version 9.3 or later.

Unless otherwise specified, continuous variables will be summarized with descriptive statistics (n, mean, median, standard deviation, standard error, minimum, and maximum), and categorical variables will be summarized with counts and percentages.

### **Definition of Baseline:**

Baseline measurements will be the last measurement for the corresponding variable prior to the first randomized dose on Visit 2, Day 0.

### **Out of Window and Unscheduled Visits:**

The protocol defined windows for scheduled visits will not be used in the analyses by visit. Data will be assigned to the scheduled visit closer in time to the scheduled visit. Unscheduled visit data will only be used in an analysis if there is no other available data closer in time to a scheduled visit. All unscheduled visit data will be included in data listings.

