## **7.4. Study Endpoints**

### **7.4.1. Primary Efficacy Endpoints**

The primary efficacy endpoints comprise a set of hypotheses that will be tested in a hierarchical fashion.

1. Mean change from baseline in average of the 3 TBUT measures in the study eye at Visit 4 (Day 84)
2. Mean change from baseline in OSDI score at Visit 4 (Day 84)
3. Mean change from Screening in Schirmer's test (anesthetized) score in the study eye at Visit 4 (Day 84).

4. Mean change from baseline in tear osmolarity in the study eye at Visit 4 (Day 84).

Groups will be compared using an analysis of covariance model where treatment group is a fixed factor and baseline score is a covariate. The treatment difference will be estimated by the adjusted least squares mean. The 95% confidence on the difference will be provided.

The differences between the 2 treatment groups will be tested with a significance level of 0.05. In order to control the Type I error rate these endpoints will be tested sequentially in the order described above. Testing will halt at the first p-value  $>0.05$ .

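### Does the SAP need a new rule on whether an early leaver's final exam counts as the Visit 4 value?

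*SAP*

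**What the plan says.** - **Endpoints.** SAP Section 7.4.1 lists four: TBUT, OSDI, Schirmer's test and tear osmolarity, each as a change to Visit 4 (Day 84). The model is: "Groups will be compared using an analysis of covariance model where treatment group is a fixed factor and baseline score is a covariate". They are tested in order, and "Testing will halt at the first p-value" above 0.05.
- **Schedule.** SAP Table 2 has one post-baseline column for these measures, shared by Visit 4 and Early Discontinuation. Visit 3 includes none of them. Protocol Sections 7.3 and 10.5 ask for the Visit 4 procedures when a subject leaves early.
- **Visit assignment.** SAP Section 7 (Out of Window and Unscheduled Visits) sets the protocol windows aside and says "Data will be assigned to the scheduled visit closer in time to the scheduled visit". Its next sentence allows unscheduled data into an analysis where no other data lie closer to a scheduled visit.
- **Missing data.** SAP Section 6 says "The planned statistical methods use all available data" and that "multiple imputation may be used for ITT analyses on the primary endpoints".
- **Populations.** The ITT "population is defined as all randomized subjects". The per-protocol set "will include all ITT subjects who remain in the study through Visit 4" and has no serious deviation. Section 7 adds: "Efficacy analysis will be conducted on the ITT population and on the PP population".

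**The concern.** An early leaver's exit exam is that subject's only post-baseline efficacy value. If the nearest-visit sentence governs, an exam before Day 63 belongs to Visit 3 or Baseline and reaches no efficacy analysis. The ITT analysis would then omit these subjects, just as the per-protocol analysis does by definition, and comparing the two would say nothing about them. Only imputation would bring them back, and it is optional.

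If the schedule governs instead, the exam is a Visit 4 value. The same data would then support two primary analyses. TBUT comes first in the sequence, so the choice could also decide whether the other three endpoints are tested.

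**Working it through.** **1. The cut-off day.** The documents do not state one. If Visit 3 counts as a candidate visit, the midpoint is (42 + 84)/2 = Day 63. If only visits that schedule TBUT and OSDI count, it is (0 + 84)/2 = Day 42. If the shared column in Table 2 governs, there is no cut-off.

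**2. The plan's own power.** Inputs from SAP Section 4: 82 per arm, two-sided 0.05; TBUT difference 2.07 s, SD 3.5; OSDI difference 11.390, SD 20.0. The noncentrality is d/(SD × √(2/n)).
- TBUT: 2.07/(3.5 × √(2/82)) = 3.79, power 96.4% (stated 95%).
- OSDI: 11.390/(20 × √(2/82)) = 3.65, power 95.2% (stated approximately 95%).

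Both figures are reproduced closely enough.

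**3. Assumptions.** The documents give no dropout rate. Take k = 4, 8 or 12 of 82 per arm (5–15%) leaving before Day 63. Let leavers show a fraction f of the planned effect. Steps 4 and 5 assume that every leaver has an exit exam.

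**4. Estimate.** With exams left out, the expected TBUT difference stays at 2.07 s. With exams counted it is 2.07 × [1 − (k/82)(1 − f)]:

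| k | f = 0 | f = 0.5 | f = 1 |
|---|---|---|---|
| 4 | 1.97 | 2.02 | 2.07 |
| 8 | 1.87 | 1.97 | 2.07 |
| 12 | 1.77 | 1.92 | 2.07 |

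**5. Power** (two-sample t-test). Left out: n = 82 − k per arm. Counted: n = 82 with f = 0, the least favourable case in the table.

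| k | TBUT left out | TBUT counted | OSDI left out | OSDI counted |
|---|---|---|---|---|
| 4 | 95.6% | 94.7% | 94.2% | 93.2% |
| 8 | 94.7% | 92.5% | 93.1% | 90.5% |
| 12 | 93.5% | 89.5% | 91.7% | 87.2% |

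**6. Chance that the two analyses disagree on TBUT.** Treat the two test statistics as bivariate normal with correlation √(nA/nB), where nA = 82 − k and nB adds the leavers who have an exam. For example, with k = 8, all examined and f = 0:
- exams left out: mean 2.07/(3.5 × √(2/74)) = 3.60
- exams counted: mean 1.87/(3.5 × √(2/82)) = 3.42
- correlation √(74/82) = 0.95
- chance that exactly one is significant: 3.5%

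Over all k and f = 0, 0.5 and 1:

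| True TBUT effect | Half of leavers examined | All examined |
|---|---|---|
| 2.07 s | 1.1–3.4% | 1.6–5.7% |
| 1.035 to 1.38 s | 4.5–9.2% | 6.2–13.2% |
| 0 | 1.5–2.6% | 2.1–3.6% |

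With only 2 leavers per arm and half examined, the figures are about 0.7% at 2.07 s and 3–4% at 1.035 to 1.38 s.

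**7. Optional imputation.** An imputation by arm from baseline alone draws the missing values around the regression line already fitted to the completers. The adjusted difference is then essentially the one from observed cases. With that model, whether imputation is run hardly moves the estimate.

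**The case for a change.** The best case for a change is this. No visible sentence assigns the exam. SAP Section 7.1 commits to documenting the per-protocol classification before unmasking, but makes no such commitment here. TBUT leads the sequence, and near the margin the disagreement can reach 13%. A few sentences would close the point, using data already collected.

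The silence stands, and so does the arithmetic. To call it a contradiction goes too far:
- The nearest-visit sentence is followed by one on unscheduled data. An early leaver has no later TBUT or OSDI, so that sentence can be read as admitting the exam.
- The schedule labels the exam as Visit 4 or Early Discontinuation, and the protocol asks for Visit 4 procedures at exit.
- Section 6's remark on available data does not address visit assignment. It is in tension with the strict reading but does not set a rival rule.

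Nor would new wording be a clear gain. Counting every exit exam lets a value after short exposure stand for 12 weeks. Counting none discards even an exam close to Day 84. Counting those nearest Day 84 drops the rest. Each is a trade-off, and nothing in the documents shows one to be wrong.

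**Conclusion.** No change follows. The SAP leaves unstated how an early-discontinuation exam maps to Visit 4, and a competent analyst can fill that gap sensibly from the schedule and the unscheduled-data sentence. Either reading gives a defensible analysis.

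The size is modest at the planned effect: about 1–6% of trials would change their TBUT verdict. TBUT power differs by 0.9 points at 5% early departure and 4.0 points at 15% (93.5 − 89.5), the latter only if every leaver is examined and shows no benefit. The exposure is larger, 4.5–13%, if the true effect is half to two-thirds of plan.

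All of this rests on assumed departure rates. The listed withdrawal criteria are withdrawn consent and loss to follow-up, where an exit exam is least certain, and both documents press sites to keep subjects in follow-up. Subjects who stop the softgels but attend Day 84 are unaffected. The table and listing shells named in SAP Section 11 were not available and may already settle the point.

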### **7.1. Subject Disposition**

Subject disposition, including the number of subjects randomized, treated, and completing the study (and completing each study visit), will be tabulated by treatment group. The percentage of subjects treated and completing the study will be based on the total number randomized. A subject data listing will be provided.

Eligibility criteria exemptions and major protocol deviations will be summarized by treatment group and presented in a listing. Major protocol deviations may include, but are not limited to the following: violation of inclusion or exclusion criteria, using prohibited medications, non-adherence to study treatment schedule. A guideline for classification of patients as belonging to the per protocol analysis dataset will be documented prior to database unmasking as will the masked review of patient data for purposes of classification.

The total number and percentage of subjects included in each of the analysis datasets will be summarized by treatment group, with percentages based on the total number of randomized subjects. A subject data listing will be provided.

Discontinuations and the reasons for discontinuation from the study will be summarized for all randomized subjects. Summaries will include the number and percentage of subjects within each treatment group.

Reasons for discontinuation following the receipt of study drug will include the following:

- Withdrawal of subject consent.
- Adverse event(s).

A subject data listing will be provided.

## **7.2. Demographic and Baseline Characteristics**

Subject demographic and baseline characteristics will be summarized for the ITT analysis population; however, should there be a reasonable difference in the size of the ITT and safety analysis populations, demographic and baseline characteristics will be summarized for both. The comparability of groups used in comparison analyses will be characterized in tables of demographic data. Summary tables will be supported with individual subject data listings.

Continuous variables such as age will be summarized using descriptive statistics (n, mean, standard deviation, median, minimum, and maximum), and categorical variables such as gender, race, ethnicity, and iris color will be summarized using counts and percentages of subjects.

Age will be determined as the whole integer number of years from the date of birth (DOB) to the date of the screening visit, i.e., the truncated integer difference between the DOB and Visit 1.

## **7.3. Treatment Compliance and Exposure**

The duration of drug exposure and % compliance will be summarized by visit and treatment group. Compliance over all visits will also be summarized.

Duration of drug exposure will be calculated for each subject as the last date of dosing minus the first date of dosing + 1. The number and percentage of subjects by treatment group will be summarized according to the following duration-of-exposure categories: '< 1 wk', '1 to < 9 wks', '9 to < 13 wks', and '≥ 13 wks'.

A subject data listing will be provided.

## **7.4. Study Endpoints**

### **7.4.1. Primary Efficacy Endpoints**

The primary efficacy endpoints comprise a set of hypotheses that will be tested in a hierarchical fashion.

1. Mean change from baseline in average of the 3 TBUT measures in the study eye at Visit 4 (Day 84)
2. Mean change from baseline in OSDI score at Visit 4 (Day 84)
3. Mean change from Screening in Schirmer's test (anesthetized) score in the study eye at Visit 4 (Day 84).

4. Mean change from baseline in tear osmolarity in the study eye at Visit 4 (Day 84).

Groups will be compared using an analysis of covariance model where treatment group is a fixed factor and baseline score is a covariate. The treatment difference will be estimated by the adjusted least squares mean. The 95% confidence on the difference will be provided.

The differences between the 2 treatment groups will be tested with a significance level of 0.05. In order to control the Type I error rate these endpoints will be tested sequentially in the order described above. Testing will halt at the first p-value  $>0.05$ .

#### **7.4.2. Exploratory Efficacy Endpoint**

- Proportion of subjects with meibomian gland dysfunction grade of 0 on both meibomian orifice size and telangiectasia scales in the study eye at Visit 4 (Day 84). Statistical significance will be assessed by a chi-square, Fisher's exact, or Cochran-Mantel-Haenszel test.

Groups will be compared using an analysis of covariance model where treatment group is a fixed factor and baseline score is a covariate. The treatment difference will be estimated by the adjusted least squares mean. The 95% confidence on the difference will be provided.

## **8. SAFETY EVALUATIONS**

### **8.1. Adverse Events**

Treatment-emergent adverse events (TEAEs) are those with onset after randomization or if occurring prior to randomization, worsened after randomization. Only treatment-emergent events will be summarized. All events in the clinical database regardless of when they occurred will be provided in data listings. Adverse events will be classified according to the Medical Dictionary for Regulatory Activities (MedDRA) system to the levels of System Organ Class (SOC) and primary Preferred Term (PT).

An overall summary will be presented which gives the number and percentage of subjects within each treatment group that experienced any TEAE, experienced any treatment related TEAE, permanently discontinued treatment due to a TEAE, experienced a treatment emergent SAE, and that died.

In summary tables, AEs occurring in both eyes will be summarized once at the greater intensity and relationship to study drug.

Events that are possibly or probably related will be counted as an event related to study drug.

The number and percentage of subjects experiencing one or more events within a MedDRA SOC and PT class without regard to intensity, relationship, or seriousness will be tabulated by treatment group. In addition, tables will display events by SOC, PT, and maximum intensity or closest relationship to treatment.

The number of deaths and SAEs will also be presented, and AEs leading to premature discontinuation from the study will be listed and tabulated.

A glossary listing that shows the verbatim terms assigned to each SOC and PT will be provided.

A listing of TEAEs by treatment group ordered by subject, SOC, PT, and onset date will be provided.

A listing of serious TEAEs by treatment group ordered by subject, SOC, PT, and onset date will be provided.

### **8.2. Concomitant Medications**

All concomitant medications listed on the case report form will be provided in data listings in the clinical study report. Each medication will be mapped to their corresponding Preferred Term from the ATC-WHO-DD (Anatomical Therapeutic Chemical World Health Organization Drug Dictionary) A frequency distribution of all concomitant medications used during the study will be provided for each treatment group. Medications used prior to randomization but stopped prior to randomization will be summarized separately from those used concomitantly. A subject data listing will be provided.

### **8.3. Ocular and Other Medical History**

History terms will be classified according to the MedDRA system to the levels of SOC and primary PT.

An overall summary will be presented which gives the number and percentage of subjects within each treatment group that experienced each condition or procedure. A subject data listing will be provided.

### **8.4. Ophthalmoscopy/Dilated Fundoscopy**

The observations of ocular ophthalmoscopy and dilated fundoscopy will be summarized in frequency tables based on the ordinal or categorical scales for each measure for each eye by time point and treatment group. A subject data listing will be provided.

**9. CHANGES FROM THE PROTOCOL**

TBD

## **10. INTERIM ANALYSIS**

No interim analyses are planned.

## **11. TABLES, LISTINGS AND FIGURES**

Table, listing and figure shells are provided in the Appendix.
